1.3. Schedule of Activities (SoA)

Schedule of Baseline Activities

Relative Day Prior to C1D1	≤28	≤14	≤7	Instructions
Procedure				
Informed consent	X			ICF must be signed before any protocol-specific procedures are performed.
Inclusion/exclusion evaluation	X			
Physical examination		X		
Height/weight and vital signs		X		Vital signs include temperature, pulse rate, pulse oximetry, respiratory rate, and blood pressure.
ECOG performance status		X		
Medical history		X		Including assessment of preexisting conditions, historical illnesses, substance usage (such as alcohol and tobacco), and other relevant habit assessments.
Cancer treatment history		X		
Concomitant medication		X		Record prior and concurrent medication/cancer treatments, includes 28 days prior to initiation of study treatments
AE collection / CTCAE grading		X		CTCAE version 5.0
Radiologic imaging		X		Baseline radiological tumor assessment per RECIST 1.1 should be done. Radiologic assessments obtained previously as part of routine clinical care up to 28 days before treatment may be used as the baseline assessment. Baseline imaging should include at minimum chest/abdomen/pelvis while follow up scans can be focused on target region of interest.
Tumor Biopsy		X		Mandatory pre-treatment biopsy. No intervening treatment between biopsy and study treatment initiation. See Section 8.8.
Archival tissue sample		X		An archival tumor sample may be requested if available and permitted by local regulations. See Section 8.8.
ECG			X	Single local ECG
ECHO		See Notes		Perform locally as clinically indicated to assess eligibility (optional) per exclusion criteria 14.j.i (See Section 5.2).
Hematology		X		See Appendix 2.
Coagulation		X		See Appendix 2.
Clinical Chemistry		X		See Appendix 2.
Urinalysis		X		See Appendix 2.
Serum pregnancy test			X	Applies to women of childbearing potential only. See Appendix 2.

Thyroid function			X	See Appendix 2.
------------------	--	--	---	-----------------

Abbreviations: AE = adverse event; C1D1 = Cycle 1 Day 1; CTCAE = Common Terminology Criteria for Adverse Events; ECG = electrocardiogram; ECHO = echocardiogram; ECOG = Eastern Cooperative Oncology Group; ICF = informed consent form; RECIST = Response Evaluation Criteria in Solid Tumors.

Schedule of On-Treatment Activities

Procedure	All Treatment Periods (Cycle = 21 days)							Notes
	Cycle 1 (± 3 days)			Cycle 2 (± 3 days)			Cycle 3-n (± 3 days)	
Relative Day within Dosing Cycle	1	8	15	1	8	15	1	
Physical exam	X	X	X	X	X	X	X	

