5.1. Inclusion Criteria

Participants are eligible to be included in the study only if all of the following criteria apply:

Age

1. Are, at the time of screening, ≥ 18 years old or of an acceptable age to provide informed consent according to local regulations, whichever is older.

Type of Participant and Disease Characteristics

2. Participants who have histological or cytological evidence of a diagnosis of a solid tumor that is advanced and/or metastatic.
 - a. Part A and B Dose-Escalation Phase:
 - The patient must have histological or cytologically proven TNBC, gastric adenocarcinoma (including gastroesophageal junction), HNSCC, cervical carcinoma, high-grade serous ovarian carcinoma, HCC, UPS, or LMS.
 - The patient must be, in the judgment of the investigator, an appropriate candidate for experimental therapy and should have progressed through or is intolerant to therapies known to confer clinical benefit (including prior IO therapies).
 - b. Part C (1 and 2) and Part D Expansion Phase (IO naïve TNBC and gastric carcinoma):
 - The patient must be, in the judgment of the investigator, an appropriate candidate for experimental therapy and should have progressed through or is intolerant to therapies known to confer clinical benefit (including IO therapies).
 - Patients with a cancer that is eligible for IO therapy based on a companion diagnostic test must have testing performed and be determined to be not eligible.
 - Gastric carcinoma patients who are microsatellite instability-high or Epstein-Barr Virus-positive will be excluded
 - Gastric carcinoma patients that have HER2 amplification should have received prior anti-HER2 therapy.
 - All patients must be PD-1/PD-L1 antagonist naïve. Patients that were not eligible for pembrolizumab based on PD-L1 expression status will be eligible for inclusion as discussed in Section 2.1.
 - Patients must have histological or cytologically proven:
 - i. Cohort C1 and D1: recurrent/metastatic, unresectable TNBC and not eligible for approved IO therapies.
 - ii. Cohort C2 and D2: recurrent/metastatic, unresectable gastric adenocarcinoma (including gastroesophageal junction)

- iii. Cohort D3: recurrent/metastatic, unresectable HNSCC, squamous cervical carcinoma, high-grade serous ovarian carcinoma, HCC, UPS, or LMS, that are associated with TIL positivity.
- Screening for TILs is required (threshold to be determined by the sponsor).

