3. Have at least 1 measurable lesion assessable using standard techniques by Response Evaluation Criteria in Solid Tumors Version (RECIST) 1.1 (Eisenhauer et al. 2009). Use of positron emission tomography scans and ultrasounds for diagnostic purposes is not permitted.
 4. Are able and willing to provide the protocol required biopsies from a newly obtained core, endoscopic, or excisional pre-treatment biopsy of a tumor lesion and a newly obtained core, endoscopic, or excisional biopsy collected during the study treatment period (see Section 8.8).
 5. Have an Eastern Cooperative Oncology Group (ECOG) performance status of 0 or 1 (Oken et al. 1982).
 6. Have discontinued all previous treatments for cancer for at least 14 days and recovered from the acute effects of therapy. Patients must have discontinued from previous treatments, as shown below:

Previous Treatment	Length of Time Prior to First Dose of Study Treatment
Cytotoxic therapies or targeted agents that are small-molecule inhibitors	≥14 days
Mitomycin-C or nitrosoureas	≥42 days
Biologic agents (for example, antibodies such as anti-PD-1 or anti-PD-L1)	≥14 days
Radiotherapy	≥28 days if greater than 30% of bone marrow is irradiated or ≥7 days if less than 30% of bone marrow is irradiated. Participants must have recovered from all radiation-related toxicities, not require corticosteroids, and not have had radiation pneumonitis.
Limited field radiotherapy for palliative intent	≥14 days
Major surgery, excluding biopsy	Patients with recent major surgery must have recovered, in the opinion of the investigator, from the toxicity and/or complications from the intervention before starting therapy.

Abbreviations: PD-1 = programmed death-1; PD-L1 = programmed death-ligand 1.

7. For Phase 1a, prior anti-PD-1 or anti-PD-L1 therapy or other immunotherapy is allowed as long as the following criteria are met:

- a. did not experience a Grade 4 immune-related toxicity or any immune-related toxicity that led to permanent discontinuation of prior anti-PD-1, anti-PD-L1, or other immunotherapy
 - b. did not experience a less than or equal to Grade 3 irAE that has not recovered to Grade 1 after use of high-dose corticosteroids that occurred during prior immunotherapy
 - i. Patients with an endocrine AE are permitted to enroll if they are stably maintained on appropriate replacement therapy and are asymptomatic
 - c. did not experience any of the following irAEs during prior anti-PD-1, anti-PD-L1, or other immunotherapy:

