7.3. Lost to Follow-Up

A participant will be considered lost to follow-up if he or she repeatedly fails to return for scheduled visits and is unable to be contacted by the study site. Site personnel are expected to make diligent attempts to contact participants who fail to return for a scheduled visit or were otherwise unable to be followed up by the site.

Site personnel, or an independent third party, will attempt to collect the vital status of the participant within legal and ethical boundaries for all participants randomized, including those who did not get investigational product. Public sources may be searched for vital status information. If vital status is determined, this will be documented and the participant will not be considered lost to follow-up.

Lilly personnel will not be involved in any attempts to collect vital status information.

Discontinuation of specific sites or of the study as a whole are handled as part of Section 10.1.7.2.

8. Study Assessments and Procedures

- Unless otherwise stated in the subsections below, all samples collected for specified laboratory tests will be destroyed within 60 days of receipt of confirmed test results. Certain samples may be retained for a longer period, if necessary, to comply with applicable laws, regulations, or laboratory certification standards.
- Study procedures and their timing are summarized in the SoA (Section 1.3). Protocol waivers or exemptions are not allowed.
- Immediate safety concerns should be discussed with the sponsor immediately upon occurrence or awareness to determine if the participant should continue or discontinue study intervention.
- Adherence to the study design requirements, including those specified in the SoA (Section 1.3), is essential and required for study conduct.
- All screening evaluations must be completed and reviewed to confirm that potential participants meet all eligibility criteria. The investigator will maintain a screening log to record details of all participants screened and to confirm eligibility or record reasons for screening failure, as applicable.
- Procedures conducted as part of the participant's routine clinical management (eg, blood count) and obtained before signing of the ICF may be utilized for screening or baseline purposes provided the procedures met the protocol-specified criteria and were performed within the time frame defined in the SoA (Section 1.3).

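### A routine-care baseline scan can predate up to 14 days of prior systemic therapy, so shrinkage from that therapy can count as response to study drug; the radiotherapy washout in criterion 6 also contradicts itself.

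*Protocol*

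**What the plan says.** In the Schedule of Baseline Activities (Protocol Section 1.3), radiologic imaging is marked in the column for 14 days or less before C1D1. The instruction beside it is wider: "Radiologic assessments obtained previously as part of routine clinical care up to 28 days before treatment may be used as the baseline assessment". The opening list of Protocol Section 8 confirms that routine procedures "obtained before signing of the ICF may be utilized for screening or baseline purposes" if they fall within the schedule's time frame. The tumour biopsy row is in the same 14-day column and carries a condition that the imaging row lacks: "No intervening treatment between biopsy and study treatment initiation".

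Washouts are in criterion 6 (Protocol Section 5.1). The lead sentence reads "Have discontinued all previous treatments for cancer for at least 14 days and recovered from the acute effects of therapy". The table beneath it gives these minimum times before first dose:

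- "Cytotoxic therapies or targeted agents that are small-molecule inhibitors": 14 days; biologic agents also 14 days; mitomycin-C or nitrosoureas 42 days.
- Radiotherapy: "≥28 days if greater than 30% of bone marrow is irradiated or ≥7 days if less than 30% of bone marrow is irradiated".
- "Limited field radiotherapy for palliative intent": 14 days.

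On prior-therapy status, criterion 2 says that the patient "should have progressed through or is intolerant to therapies known to confer clinical benefit".

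Protocol Section 9.4.3.2 defines change in tumour size as percent change from the baseline evaluation, not from C1D1. Protocol Section 9.5 and SAP Section 5.8 plan a review of safety, efficacy and PK/PD in each of Cohorts D1 and D2 at about the first 20 patients, to decide whether to enrol up to about 40.

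**The concern.** The oldest acceptable routine scan (28 days) is older than the shortest systemic washout (14 days), and no rule ties the two together. A patient can be scanned, receive further prior therapy, stop it, and start study drug with every criterion met. Any tumour change caused by that intervening therapy lies between the baseline measurement and the first on-study scan, and the analysis will credit it to LY3435151, alone or with pembrolizumab.

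The endpoints exposed are those that compare tumour burden with baseline: ORR, disease control rate and change in tumour size. They matter most at the 20-patient review in D1 and D2, which has no stated numerical response threshold and no pembrolizumab-alone arm for reference, so one or two responses may weigh heavily.

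A second problem lies in the same eligibility criterion. The three statements on prior radiotherapy do not agree. A limited palliative field covering less than 30% of marrow fits both the 7-day row and the 14-day row, and the lead sentence requires 14 days for everything. Section 5 does not permit eligibility waivers, so a site cannot tell whether a patient irradiated 10 days earlier may enter.

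**Working it through.** **1. The plan's own figures.** The only statistical figures bearing on response are the exact (Clopper-Pearson) 95% intervals in Protocol Section 9.2 and SAP Table JZIA.5.1. Recomputed from beta quantiles, all ten match to two decimals, for example 0/20: 0 to 0.17; 3/20: 0.03 to 0.38; 5/20: 0.09 to 0.49. The table is not in dispute.

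**2. Length of the overlap.** Overlap = maximum age of routine scan − minimum washout.

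- Cytotoxic, small-molecule targeted, biologic: 28 − 14 = 14 days.
- Limited-field palliative radiotherapy, or any radiotherapy under the 14-day lead sentence: 28 − 14 = 14 days.
- Radiotherapy to more than 30% of marrow: 28 − 28 = 0 days.
- Mitomycin-C or nitrosoureas: 42 exceeds 28, so none.

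With the scheduled scan (14 days or less before C1D1), the systemic-therapy overlap is 14 − 14 = 0. The systemic problem therefore comes only from the routine-scan allowance.

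**3. A compliant sequence.** Routine scan on day −28, chemotherapy to day −15, biopsy on day −10, first dose on Day 1. The scan is within 28 days, the washout is at least 14 days, the biopsy is within 14 days, and no treatment falls between biopsy and dosing. The chemotherapy still comes after the baseline scan.

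**4. Effect on the response threshold.** The protocol's iRECIST text (Section 8.1.1) uses a 30% decrease from baseline for partial response. If the target-lesion sum has already fallen by a fraction s before C1D1, the further shrinkage needed is 1 − 0.70/(1 − s). The values of s are assumptions:

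- s = 0.10: 1 − 0.70/0.90 = 22.2%.
- s = 0.20: 1 − 0.70/0.80 = 12.5%.

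**5. Weight of one carried-over response.** 1/8 = 12.5 points (one Stage 1 arm), 1/20 = 5 points, 1/30 = 3.3 points (D3), 1/40 = 2.5 points. At the 20-patient review, 0/20 (0 to 0.17) would become 1/20 = 0.05 (0.001 to 0.25).

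**6. Chance of at least one.** The documents give no rate, so q, the per-patient probability of a carried-over response, is assumed. P = 1 − (1 − q)^n.

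| q | n=20 | n=40 |
|---|---|---|
| 1% | 18.2% | 33.1% |
| 2% | 33.2% | 55.4% |
| 5% | 64.2% | 87.1% |
| 10% | 87.8% | 98.5% |

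These figures show sensitivity to q and are not an estimate of the bias.

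**The case against.** The best case for the plan has several parts.

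- *The default is already right for systemic therapy.* The scheduled scan sits in the 14-day column and cannot precede systemic therapy that ended at least 14 days before dosing. This stands, and it confines the systemic point to reused routine scans.
- *The biopsy rule bars late treatment.* It bars treatment after the biopsy only. The sequence in the working satisfies it.
- *Patients should have progressed on prior therapy.* That makes continued treatment after the qualifying scan less typical, but intolerance also qualifies, so a patient stopping an active drug can enter.
- *Exclusion 19 lets the investigator exclude confounding therapy.* It is discretionary and says nothing about scan timing.
- *Responses must be confirmed.* Both determinations are compared with the same baseline, so confirmation does not help.
- *Treatments in the prior 28 days are recorded.* Affected patients could be identified, but no analysis rule uses that record.
- *Response is a secondary objective, estimated without a formal test, and the review weighs safety and PK/PD as well.* This stands. It limits the consequence, as does the protocol's statement that its interval table is a reference for estimation and not a basis for decisions.

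A reader might infer more than the documents support. A 21-day overlap (28 − 7) follows only if the 7-day radiotherapy row governs, and the lead sentence of the same criterion contradicts that row. That case would also need the mandatory biopsy to fall in the last week before dosing. A reader might also infer that a rule on previously irradiated target lesions is missing. Lesion assessment is delegated to RECIST 1.1, whose text is not in the documents, so the omission cannot be shown.

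**Conclusion.** The gap is real but narrow. Under the routine-scan allowance, up to 14 days of cytotoxic, targeted or biologic therapy can fall between the baseline scan and first dose, and neither document prevents it. Prior-therapy shrinkage can then enter ORR, disease control rate, change in tumour size and the D1/D2 review. Each affected response is worth 5 points at n=20 and 2.5 at n=40.

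The size of the bias cannot be computed, because the documents give neither the share of patients with such scans nor a carry-over rate. It would be wrong to read all efficacy endpoints as measured from the baseline scan: PFS runs from start of treatment and duration of response from first response, so they are affected only through how response and progression are scored. The primary safety objective is not affected.

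The radiotherapy statements in criterion 6 are a separate and definite contradiction in an eligibility rule. This review takes no position on which interval should apply.

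**What to change.** In the Radiologic imaging row of the Schedule of Baseline Activities, state that a routine-care scan may serve as baseline only if it was taken after the last dose or fraction of prior anticancer therapy, with no anticancer treatment between the scan and C1D1. Otherwise the scheduled scan must be done, also after the last prior treatment. This applies to imaging the principle that the biopsy row already uses.

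The overlap then falls from up to 14 days to 0. The change does not remove residual effects of a drug already stopped, or tumour growth between an older scan and Day 1. The cost is one sentence and a repeat scan for the few patients whose routine scan predates their last therapy. No sample size changes.

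In criterion 6, reconcile the lead sentence, the Radiotherapy row and the limited-field palliative row so that one minimum applies to any given field. The sponsor must decide which.

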Urinalysis	X			X			X	See Appendix 2. If baseline laboratory tests were performed ≤3 days prior to C1D1 and the results are deemed to be clinically valid by the investigator, laboratory tests do not need to be repeated on

Procedure	All Treatment Periods (Cycle = 21 days)							Notes
	Cycle 1 (± 3 days)			Cycle 2 (± 3 days)			Cycle 3-n (± 3 days)	
Relative Day within Dosing Cycle	1	8	15	1	8	15	1	
								C1D1.
Serum or urine pregnancy test	X			X			X	See Section 8.3.4 and Appendix 2. If baseline laboratory tests were performed ≤3 days prior to C1D1 and the results are deemed to be clinically valid by the investigator, laboratory tests do not need to be repeated on C1D1.
Coagulation	See Notes							Collect as clinically indicated
Stool sample	See Section 1.3.1							Refer to Section 1.3.1 for sample collection time points
Plasma sample	See Section 1.3.1							Refer to Section 1.3.1 for sample collection time points
On-treatment tumor biopsy				X				Mandatory on-treatment biopsy on C2D1 for all patients except during dose escalation Cohorts A1, A2, and A3. See Section 8.8.
Optional tumor biopsy	See Notes							An optional tumor biopsy may be performed, if clinically feasible, after disease progression or at additional study time points, if warranted and agreed upon by the investigator and Lilly.
Radiologic imaging	See Notes							Scans will be performed and reviewed locally; done every 6 weeks ± 7 days from Cycle 1 Day 1 for 36 weeks. Afterwards, perform every 9 weeks ±7 days. The same method of assessment and technique used at baseline should be used for each consecutive assessment thereafter. RECIST 1.1/iRECIST should be used for all tumors.
AE Collection / CTCAE Grading	See Notes							CTCAE version 5.0. Evaluated at each visit and continuously throughout study. See Section 8.3 for more information about adverse events and adverse event collection.
Concomitant Medication Notation	See Notes							Evaluated at each visit and throughout study. Refer to Section 6.5 for more information about concomitant medications.
Administer LY3435151	X			X			X	Administer Q3W per Section 6.1. May be administered up to 3 days prior to scheduled visit.
Administer pembrolizumab	X			X			X	For Dose Escalation Part B and Dose Expansion Part D, administer Q3W per Section 6.1. May be administered up to 3 days prior to scheduled visit.

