8.1. Efficacy Assessments

Tumor assessments will be performed for each patient at the times shown in the SoA (Section 1.3).

Response Evaluation Criteria in Solid Tumors v1.1 (Eisenhauer et al. 2009) and iRECIST (Seymour et al. 2017) will be applied as the primary criteria for assessment of tumor response and date of tumor progression. The method of tumor assessment used at baseline must be used consistently throughout the study. Local tumor imaging (investigator assessment with site radiological reading) will be used. See Section 8.1.1 for detailed information regarding iRECIST for immune-based therapies.

Computed tomography (CT) scans, including spiral CT, are the preferred methods of measurement (CT scan thickness recommended to be ≤ 5 mm); however, magnetic resonance imaging is also acceptable in certain situations, such as when body scans are indicated or if there is a concern about radiation exposure associated with CT. Intravenous and oral contrast are required unless medically contraindicated.

See Section 9.4.3 for definitions of the efficacy endpoints.

8.1.1. iRECIST for Immune-Based Therapies

Rationale of Using iRECIST after First Radiologic PD by RECIST 1.1

The response to immunotherapy may differ from the typical responses observed with cytotoxic chemotherapy, including the following (Wolchock et al. 2009; Nishino et al. 2013):

- Response to immunotherapy may be delayed.
- Response to immunotherapy may occur after progressive disease by conventional criteria.
- The appearance of new lesions may not represent progressive disease with immunotherapy.

Therefore, to adequately characterize additional patterns of response and progression specific to patients treated with immunotherapy, which cannot be captured using conventional criteria such as RECIST v1.1, alternative measures of tumor assessment have been developed. The iRECIST standard was developed by the RECIST working group for the use of modified RECIST version 1.1 in cancer immunotherapy trials (Seymour et al. 2017).

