After initial disease progression defined by RECIST 1.1, iRECIST guidelines will be applied in the following tumor assessments. In iRECIST, any new lesions are categorized as measurable or non-measurable. Up to 5 lesions total (up to 2 per organ) can be selected as new lesion-target (NL-T). All other new lesions will be followed as new lesion-non-target (NL-NT). The NL-T sum of diameters will be calculated and recorded separately from the sum of diameters for target lesions identified at baseline.

Tumor response by iRECIST will be classified as confirmed progression (iCPD), or unconfirmed progression (iUPD), or stable disease or response (iSD/iPR/iCR) at all subsequent imaging. The initial tumor scan showing disease progression by RECIST 1.1 will be assigned as unconfirmed progression (iUPD) for overall response.

Progression is considered confirmed (iCPD), if the previous response status was iUPD and any of the following happens:

- For target lesions: any further increase in the previously identified target lesion sum of diameters by 5mm or more after iUPD.
- For non-target lesions: any further increase in the size of previously identified non-target lesion iUPD (the increase doesn't need to meet RECIST 1.1 criteria for unequivocal progression)
- For new lesions:
 - an increase in the NL-T previously identified as iUPD and increase ≥ 5 mm in sum of diameter OR
 - any increase for NL-NT OR
 - any appearance of additional new lesions

The overall response remains iUPD, IF

- target lesions were the cause of the initial iUPD AND
- target lesions haven't worsened, but they are still above PD threshold (20% increase from the nadir), AND
- no above factors of iCPD occur.

When progression is considered not unconfirmed, the overall response can become iSD/iPR/iCR instead of iUPD if any of the following criteria are met:

- iCR: Target lesions and non-target lesions have regressed completely AND no new lesions.
- iPR: Target lesions have regressed to $\geq 30\%$ decrease from baseline (iCR or iPR) AND non-target lesions remain non-iCR/non-iUPD AND no new lesion
- iSD: Target lesions have regressed to $< 20\%$ increase from nadir AND non-target lesions remain non-iCR/non-iUPD AND no new lesion.

Imaging and Treatment Guideline for Patients Who Have Radiologic Evidence of Progressive Disease by RECIST 1.1

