Situation^a	Event/Censor	Date of Event or Censor
Tumor progression or death	Event	Earliest date of progressive disease or death
No tumor progression and no death	Censored	Date of last adequate tumor assessment per RECIST 1.1, or date of first dose (whichever is later) ^b
Unless		
No baseline radiologic tumor assessment available	Censored	Date of first dose
No adequate postbaseline tumor assessment available and death reported after 2 scan intervals following the first dose ^{b, c}	Censored	Date of first dose
Tumor progression or death documented immediately after 2 or more scan intervals following last adequate tumor assessment or randomization (whichever is later) ^{b,c}	Censored	Date of last adequate tumor assessment, per RECIST 1.1, or date of first dose (whichever is later) ^b
New therapeutic anticancer treatment started prior to tumor progression or death	Censored	Date of last adequate radiological assessment prior to new therapeutic anticancer therapy ^b

Abbreviations: CR = complete response; PFS = progression-free survival; PR = partial response; RECIST = Response Evaluation Criteria in Solid Tumors; SD = stable disease.

- ^a Symptomatic deterioration (ie, symptomatic progression that is not confirmed per RECIST 1.1) will not be considered as tumor progression.
- ^b Adequate tumor assessment per RECIST 1.1 refers to an assessment with one of the following responses: CR, PR, SD, or PD.
- ^c Refer to the statistical analysis plan for the definition of 2 scan intervals, including any adjustment for scan window.

Time to response (TTR) is defined as the time from the date of start of treatment to the date measurement criteria for confirmed CR or PR (whichever is first recorded) are first met. For patients who are not known to have achieved CR or PR as of the data inclusion cut-off date, TTR will be censored at the date of the last objective disease assessment prior the date of any subsequent systematic anticancer therapy.

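### Follow-up scans may be limited to an undefined target region, so new lesions and non-target progression elsewhere cannot be assessed; response and PFS endpoints can be overstated by an unknown amount.

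*Protocol*

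**What the plan says.** **Extent of imaging.** Protocol 1.3, Schedule of Baseline Activities, Radiologic imaging row: "Baseline imaging should include at minimum chest/abdomen/pelvis while follow up scans can be focused on target region of interest". No section defines the target region, and neither document states follow-up coverage anywhere else.

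**Schedule and criteria.** The on-treatment imaging row in Protocol 1.3 has scans "done every 6 weeks ± 7 days from Cycle 1 Day 1 for 36 weeks", then every 9 weeks, and applies RECIST 1.1/iRECIST to all tumors. It adds: "The same method of assessment and technique used at baseline should be used for each consecutive assessment thereafter". Protocol 8.1 says: "The method of tumor assessment used at baseline must be used consistently throughout the study".

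**What decides response.** Under Protocol 8.1.1, growth of non-target lesions confirms progression after iUPD, and so does "any appearance of additional new lesions". Complete response is defined as "iCR: Target lesions and non-target lesions have regressed completely AND no new lesions". iPR and iSD likewise require that no new lesion is present and that non-target disease has a known status.

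**What counts as adequate.** Footnote b of the PFS censoring table in Protocol 9.4.3.2 reads: "Adequate tumor assessment per RECIST 1.1 refers to an assessment with one of the following responses: CR, PR, SD, or PD". SAP Table JZIA.5.2 repeats this in substance, and SAP Table JZIA.5.3 does the same for iPFS with the iRECIST categories. None of the three mentions coverage.

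**Who reads.** Protocol 8.1: "Local tumor imaging (investigator assessment with site radiological reading) will be used". No central review is described.

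**The concern.** A site that uses the permission images part of the body and then has to record whether new lesions are present anywhere. If it records none, the patient is classed as SD, PR or CR without the rest of the baseline field having been examined. Progression that starts outside the region is then dated late or not at all, and a patient with a mixed response can be counted as a responder or as disease control.

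ORR, DCR, DoR and PFS are secondary endpoints; iORR, iPFS and iDoR are exploratory. Efficacy in about the first 20 combination patients also informs the D1 and D2 reviews on whether to go on to about 40 (Protocol 9.5, SAP 5.8). The loss cannot be made good later, because no re-reading or analysis rule recovers regions that were never imaged.

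**Working it through.** **1. The rules side by side**

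| Fact needed (Protocol 8.1.1) | Can a target-region scan supply it? |
|---|---|
| Size of target lesions inside the region | Yes |
| Status of non-target lesions outside the region | No |
| Absence of new lesions (iCR, iPR, iSD) | Not outside the region |
| Further new lesions confirming progression | Not outside the region |
| Assessment adequate for PFS or iPFS | Yes, once a category is recorded |

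The last row is the problem: the footnotes accept a category that the scan could not support.

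**2. The plan's own figures.** The only numerical basis for response is the Clopper-Pearson table (Protocol 9.2, SAP Table JZIA.5.1). With lower limit Beta(0.025; x, n−x+1) and upper limit Beta(0.975; x+1, n−x), 5/40 gives 0.042 to 0.268 (plan 0.04 to 0.27) and 10/40 gives 0.127 to 0.412 (plan 0.13 to 0.41). All ten rows reproduce to two decimals. These limits describe sampling error only, not misclassification.

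**3. Weight of one patient.** 1/40 = 2.5 points; 1/20 = 5 points at the interim review; 1/8 = 12.5 points in C1 or C2. If 2 of 10 apparent responders out of 40 had unseen progression before confirmation, 10/40 = 25% (95% CI 13% to 41%) should have been 8/40 = 20% (9% to 36%).

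**4. Illustration of direction and range.** The documents give no rate for progression outside the target region, so every rate here is an assumption: true median time to progression m = 2, 4 or 6 months; a share s = 10% to 50% of the progression hazard arising only outside the region; median survival 12 months; 25% of patients with target shrinkage first seen at scans 1 to 3; focused scans used for everyone; no outside progression detected. The scan times are the protocol's.

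The DCR proxy (alive with no detected progression at the first scan) has a closed form. The first scan falls at 6 × 7 / 30.4375 = 1.38 months, so

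DCR = 2^(−1.38(1−s)/m) × 2^(−1.38/12), with s = 0 for full coverage.

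For m = 4: full coverage 0.787 × 0.923 = 0.727; focused with s = 0.2, 0.826 × 0.923 = 0.763. Simulation (100,000 patients per scenario) agrees to rounding and adds the other endpoints:

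| m (months) | s | Median PFS, full → focused (months) | DCR proxy (%) | Confirmed ORR (%) | iORR (%) |
|---|---|---|---|---|---|
| 2 | 10% | 2.8 → 2.8 | 57.1 → 60.0 | 5.1 → 5.9 | 9.0 → 9.8 |
| 2 | 30% | 2.8 → 2.8 | 57.0 → 65.8 | 5.3 → 7.9 | 9.2 → 11.8 |
| 2 | 50% | 2.8 → 3.6 | 57.1 → 72.6 | 5.2 → 9.9 | 9.1 → 13.7 |
| 4 | 20% | 3.7 → 4.1 | 72.7 → 76.4 | 9.8 → 11.3 | 13.5 → 14.8 |
| 4 | 50% | 3.7 → 5.5 | 72.6 → 82.0 | 9.9 → 13.8 | 13.6 → 17.0 |
| 6 | 10% | 4.1 → 4.6 | 78.7 → 80.0 | 12.4 → 13.0 | 15.7 → 16.1 |
| 6 | 50% | 4.1 → 6.4 | 78.7 → 85.3 | 12.6 → 15.7 | 15.9 → 18.5 |

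Median DoR and iDoR did not move for m = 2 with s of 10% to 30%, and were longer under focused scanning in the other scenarios. No endpoint was lower under focused scanning in any scenario. Universal use and zero detection are worst-case settings, so for given m and s these shifts are upper ends, not expected values.

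**The case against.** The wording is permissive, it sits in the baseline row, and the region could be read broadly. Sites may scan the full field throughout, and the on-treatment row still demands RECIST 1.1/iRECIST. Some events are caught anyway: deaths count for PFS and iPFS, physical examinations are scheduled at every listed on-treatment visit, and nothing forbids imaging a symptomatic site, which can then yield a RECIST event. The PFS definition even mentions clinical progression, although footnote a of the same table excludes symptomatic deterioration not confirmed per RECIST 1.1. The endpoints are secondary or exploratory, no response-rate hypothesis is tested, and the CI table is offered as a reference rather than a decision basis.

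All of that stands as a limit on size and importance. None of it makes a narrow scan able to show that no new lesion exists elsewhere, or makes such a scan inadequate.

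Two stronger readings are tempting. One is that every efficacy endpoint *is* overstated. The documents do not support it. Use of the permission is optional. Confirmed ORR rises only if unseen progression precedes the confirming scan, and iORR only if it precedes the first iPR or iCR. iDoR also depends on which false responders are added, and no mechanism is shown for TTR. The other is that the consistency rules in the on-treatment row and Protocol 8.1 flatly contradict the permission. They concern method and technique, and the text that follows in 8.1 is about CT versus MRI, slice thickness and contrast. They do not state coverage, so they neither contradict the permission nor repair it. The real conflict is with the lesion rules in 8.1.1.

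**Conclusion.** The point holds as a defect in the imaging rule. Follow-up limited to an undefined target region is incompatible with RECIST 1.1/iRECIST as this protocol applies them, and the adequacy footnotes let such scans through. Where the permission is used, PFS, DCR, ORR, DoR and their iRECIST versions can be overstated; the risk runs towards better-looking results.

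The size is unknown. Under the assumptions above it ran from no change in some medians to 6.4 − 4.1 = about 2.3 months in median PFS, 72.6 − 57.1 = about 15 points in DCR and 9.9 − 5.2 = about 5 points in ORR, with iORR similar. No single row should be read as the expected inflation in this trial. The primary safety and DLT objectives and OS do not depend on scan coverage. The practical consequence lies in the secondary efficacy estimates and in the D1/D2 interim review, where efficacy is weighed with safety and PK/PD.

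**What to change.** 1. Protocol 1.3, baseline imaging row: delete the second half of the sentence, which allows focused follow-up scans.
2. Protocol 1.3, on-treatment imaging row: state that follow-up scans cover at least the regions imaged at baseline, meaning chest, abdomen and pelvis plus any other site of disease at baseline.
3. Footnote b in the PFS table of Protocol 9.4.3.2 and in SAP Tables JZIA.5.2 and JZIA.5.3: state that an assessment not covering those regions may establish PD (iUPD or iCPD) but is not adequate for CR, PR or SD (iCR, iPR or iSD).

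The third change is needed as well as the first two; otherwise the schedule and the footnotes would carry different definitions of an adequate assessment.

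The cost is a wider field at scan visits already planned, with some added radiation and burden; Protocol 8.1 already accepts MRI where radiation from CT is a concern. A few narrow scans will become inadequate, which can bring the two-scan-interval censoring rule into play. Visit timing does not change. The amendment should precede further scans, since missing regions cannot be recovered.
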